
Statistical methods:
 
PK parameters will be analysed after logarithmic transformation and 90% confidence intervals (CIs) for the geometric means. The conclusions regarding possible differences between different study treatments will be based on both overall evaluation of levodopa concentration-time profiles and formal statistical analyses of PK parameters.
 
Primary pharmacokinetic evaluation
 
The primary PK variable will be summarised using descriptive statistics by treatment and analysed using a mixed linear model with 90% CI applicable for the crossover design. The statistical model will include treatment and period as fixed effects and subject as random effect. Sensitivity analysis adjusted for subject weight and age will be performed. The primary conclusions will be based on the per-protocol (PP) population.
 
Secondary pharmacokinetic evaluation
 
Statistical evaluation of the secondary PK variable will be done using similar methods to the primary variable. Statistical model for $C_{min,tau}$ will include treatment, period, dosing interval and treatment by dosing interval interaction as fixed effects and subject by period interaction as random effect.
 
Other pharmacokinetic evaluations
 
PK variables for the evaluation of PK of levodopa, carbidopa, 3-OMD and ODM-104 will be summarised by treatment using descriptive statistics. Selected PK variables will be analysed using similar models and sensitivity analysis to the primary and secondary PK variables. Drug concentrations will be tabulated by time and treatment with descriptive statistics.

Safety evaluation

AEs and serious adverse events (SAEs) will be summarised by treatment using subject and event counts. Clinical safety variables and their changes from baseline will be evaluated using descriptive statistics. 12-lead ECG abnormalities will be tabulated and the intra-subject differences between visits will be evaluated. Laboratory safety variables will be evaluated using descriptive statistics for the actual values and their changes from baseline. Physical examination and C-SSRS findings will be tabulated.

ABBREVIATIONS AND DEFINITION OF TERMS

3-ODM	3-O-methyldopa
AADC	Aromatic l-amino acid decarboxylase
AE	Adverse event
AUC	Area under the concentration-time curve
BMI	Body mass index
BP	Blood pressure
CA	Competent authority
CI	Confidence interval
C _{max}	Maximum concentration in plasma
C _{min}	Minimum concentration in plasma

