5.3 Selection and timing of doses

Overall, MR levodopa strength will be 50, 100 or 150 mg, carbidopa strength will be 12.5, 25 or 65 mg and ODM-104 strength will be 0, 50 mg or 100 mg. Sinemet contains 100 mg of IR levodopa and 25 mg of carbidopa.

The strength of levodopa, carbidopa and ODM-104 will depend on the parallel group (Groups 1-4) the study subject has been assigned to. The doses during the 4 treatment periods are presented in [Table 1](#) in section [3.2](#).

In all parallel groups, depending on the treatment period, carbidopa with or without ODM-104 will be taken 4 times a day during the days 1-6. On day 7 (PK sampling day), carbidopa with or without ODM-104 will be taken at the same time with levodopa 4 times a day. The duration of treatment will be 7 days for carbidopa and ODM-104 and 1 day for levodopa. In one of the periods in Group 4, Sinemet will be taken on day 7 without ODM-104 and on days 1-6, only carbidopa 25 mg will be administered.

The selected strengths and dosing regimens are based on previous PK studies in healthy subjects conducted during ODM-104 development program and other levodopa programs.

Carbidopa and ODM-104 (in treatment periods including ODM-104) will be taken 4 times a day – first dose, 3.5 h, 7 h and 10.5 h doses, for 6 days. The study treatments should be taken

at the same time every day to provide even concentrations of the active ingredients. The recommended study treatment intake times on days 1-6 are 8:00, 11:30, 15:00 and 18:30 h.

Subjects will arrive at the study centre in the evening before day 1 (day -1) and stay at the study centre until the 24 h PK blood sample has been drawn in the morning of day 8. Subjects will take all study treatments at the study centre.

In the evening of day 6, subjects will start fasting for at least 10 h (from around 22:00 h on day 6) before the first morning dose (0 h) at approximately 8:00 h on day 7. Drinking of water is permitted until 1 h before dosing.

The recommended study treatment intake times on day 7 are the same as those on the previous 6 days: 8:00, 11:30, 15:00 and 18:30 h. Study treatments will be ingested with 200 ml of water. Study subjects should maintain an upright position (sitting or standing) for at least 1 h after the study treatment administration and as much as possible during the day until 24:00 h.

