6.1.2.2 Days 2-5

The following procedures on days 2-5 will be performed:

- Subjects will take carbidopa and ODM-104 (on study periods including ODM-104) similar to day 1 and as described in section 5.3.
- Meals will be served as described in section 5.3.
- AEs, current medical conditions and concomitant treatments will be recorded.

6.1.2.3 Day 6

The following procedures on day 6 will be performed:

- Subjects will take carbidopa and ODM-104 (on study periods including ODM-104) similar to day 1 and as described in section 5.3.
- HR and BP will be recorded in the supine position after at least 5 min rest 1-2 h after the 7 h dose.
- 12-lead ECG will be recorded in the supine position after at least 5 min rest 1-2 h after the 7 h dose.
- Meals will be served as described in section 5.3.
- Current medical conditions and concomitant treatments will be recorded.
- AEs will be recorded.

6.1.2.4 Day 7

Subjects will fast from 22:00 h (10 h) on day 6 until breakfast on day 7, except that drinking of water is permitted up to 1 h before dose.

- BP and HR will be recorded in the supine position after at least 5 min rest 0-2 h before the first dose and 1-2 h after the 7 h dose.
- 12-lead ECG will be recorded in the supine position after at least 5 min rest 0-2 h before the first dose and 1-2 h after the 7 h dose.
- Blood samples for selected haematology and clinical chemistry tests will be collected before the first dose; see section 6.4.5 for details.
- Urinalysis will be performed.
- C-SSRS will be performed.
- Subjects will take the first dose (levodopa, carbidopa and possible ODM-104) approximately at 8:00 h after the pre-dose PK blood sampling. All study treatments will be taken precisely at the planned time points, including time points coinciding with PK blood sampling; see section 5.3 for details.
- Blood samples for PK assessments will be collected; see section 6.2.1 for details.
- Meals will be served as described in section 5.3.
- AEs, current medical conditions and concomitant treatments will be recorded.

6.1.2.5 Day 8

- Blood sample for 24-h PK assessments will be collected in the morning of day 8; see section 6.2.1 for details.
- Subjects will be instructed to call the study centre when they experience any AE or need to take any concomitant treatment until the end-of-study visit when the subjects are not in-house.
- Subjects can leave the study centre after the 24 h PK blood sample has been collected.

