6.2 Pharmacokinetic assessments

6.2.1 Blood sampling

Peripheral venous blood samples will be drawn for the determination of concentrations of levodopa, carbidopa, 3-OMD and ODM-104 in plasma. For blood sampling, a forearm vein will be cannulated. Blood samples will be drawn before the drug administration (0 h) and at 0.5, 1, 1.5, 2, 2.5, 3, 3.5, 4, 4.5, 5, 5.5, 6, 6.5, 7, 7.5, 8, 8.5, 9, 9.5, 10, 10.5, 11, 11.5, 12, 12.5, 13, 13.5, 14, 15, 16 and 24 h after the drug administration. At time points 3.5, 7 and 10.5 h, the study treatment will be administered and the blood sample drawn at a same time. However, exact timing of study treatment administration will be prioritised, e.g. in case of problems in blood sampling.

Before the start of the study, detailed instructions for collecting, handling, storing and shipping of the plasma samples will be provided to the study centre. Maximum volume of blood collected in the study is provided in the subject information.

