$C_{\max}/C_{\min,\tau}$	Ratio of the maximum observed concentration in each dosing interval and the observed concentration at the end of each dosing interval
$C_{\max}/C_{\min,\tau,\text{actual}}$	Ratio of the maximum observed concentration in each dosing interval and the observed minimum plasma concentration after each dose before the concentration starts to rise due to the following dose. For the 4th dosing interval the plasma concentration at time 16 h was used as the minimum plasma concentration
$C_{\max}/C(16\text{h})$	Ratio of the maximum observed concentration from time 0 to 16 h and the observed concentration at time 16 h
PTF_{τ}	Peak-trough fluctuation for each dosing interval, calculated by $(C_{\max,\tau} - C_{\min,\tau}) \times 100 / C_{\text{av},\tau}$, where the average concentration, $C_{\text{av},\tau} = \text{AUC}_{\tau} / \text{duration of dose interval}$
PTF_{0-16}	Peak-trough fluctuation, calculated by $(C_{\max} - C_{\min}) \times 100 / C_{\text{av}}$, where the average concentration, $C_{\text{av}} = \text{AUC}_{0-16} / 16 \text{ h}$

The PK parameters will be calculated with non-compartmental methods using PhoenixTM WinNonlin[®] Build 6.3.0.395 or a later software version (Certara L.P., USA). The actual time of sampling will be used in the calculation of PK parameters. Possible outlying concentrations excluded from the PK analysis will be reported and justified in the study report.

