8.4.3 Pharmacokinetic analysis

The primary variable for the evaluation of PK of levodopa is AUC_{0-24} to describe the total levodopa exposure. The secondary PK variable is $C_{min,tau}$, which is used to describe minimum concentration during the dosing intervals. The ratio of the C_{max} in a dosing interval and the observed concentration at the end of the dosing interval, $C_{max}/C_{min,tau}$, which is used to describe levodopa fluctuation during the dosing intervals and other PK variables of levodopa, 3-OMD, carbidopa and ODM-104 will be evaluated as other variables.

PK parameters will be analysed after logarithmic transformation and 90% confidence intervals (CIs) for the geometric means will be calculated.

The conclusions regarding possible differences between different study treatments will be based on both overall evaluation of levodopa concentration-time profiles and formal statistical analyses of PK parameters.

Primary pharmacokinetic evaluation

The primary PK variable will be summarised using descriptive statistics by treatment and analysed using a mixed linear model with 90% CI applicable for the crossover design. The statistical model will include treatment and period as fixed effects and subject as random effect. Sensitivity analysis adjusted for subject weight and age will be performed.

Levodopa fluctuation ratios ($C_{\max}/C_{\min,\tau}$, $C_{\max}/C_{(16\text{ h})}$, PTF_{τ} and PTF_{0-16}), and AUC_{0-24} , C_{\max} and $C_{\min,\tau}$ will be the main PK variables of interest.

The primary conclusions will be based on the PP population.

Secondary pharmacokinetic evaluation

Statistical evaluation for secondary PK variable will be done using similar methods as for primary variable. Statistical model for $C_{\min,\tau}$ will include treatment, period, dosing interval, and treatment by dosing interval interaction as fixed effect and subject by period interaction as random effect.

Other pharmacokinetic evaluations

The other PK variables for the evaluation of PK of levodopa, carbidopa, 3-OMD and ODM-104 are presented in [Table 4](#). All PK variables will be summarised by treatment using descriptive statistics. Selected PK variables will be analysed using similar models and sensitivity analysis to the primary and secondary PK variables. Drug concentrations will be tabulated by time and treatment with descriptive statistics.

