## 1 Abbreviations

|                  |  |
|------------------|--|
| AE               | Adverse event                              |
| AUC              | Area under the concentration-time curve    |
| BMI              | Body mass index                            |
| BP               | Blood pressure                             |
| C max | Peak concentration in plasma               |
| C min | Minimum observed concentration             |
| CV               | Coefficient of variation                   |
| ECG              | Electrocardiogram                          |
| HR               | Heart rate                                 |
| IR               | Immediate release                          |
| ITT              | Intention-to-treat                         |
| MR               | Modified release                           |
| PD               | Parkinson's disease                        |
| PG               | Pharmacogenomic(s)                         |
| PK               | Pharmacokinetic(s)                         |
| PP               | Per-protocol                               |
| SAE              | Serious adverse event                      |
| t ½   | Terminal elimination half-life             |
| t max | Time to reach peak concentration in plasma |

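### Read literally, PTF0-16 takes the pre-levodopa sample as its trough and reduces to Cmax/Cav; Cmin needs a post-dose definition, and PTFtau needs a rule for zeros

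*Protocol*

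**What the plan says.** **The index.** Protocol 6.2.3, Table 4, gives PTF0-16 as "Peak-trough fluctuation, calculated by" the difference between Cmax and Cmin, times 100, divided by Cav, where Cav is AUC0-16 over 16 h. PTFtau has the same form within each dosing interval, with Cmax,tau, Cmin,tau and Cav,tau.

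**The trough.** Table 4 defines Cmin,tau (the samples at 3.5, 7, 10.5 and 14 h) and Cmin,tau,actual. It does not define plain Cmin. The only meanings given are in the abbreviation lists: "Minimum concentration in plasma" in the Protocol and "Minimum observed concentration" in the SAP. Neither gives a time window or excludes a sample.

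**Dosing and sampling.** Protocol 5.3: "The duration of treatment will be 7 days for carbidopa and ODM-104 and 1 day for levodopa". Protocol 6.1.2.4 (Day 7): "Subjects will take the first dose (levodopa, carbidopa and possible ODM-104) approximately at 8:00 h after the pre-dose PK blood sampling". Protocol 6.2.1 counts that 0 h sample as part of the PK profile. Protocol 1.2.1 requires at least 4 days of wash-out between treatments.

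**Analysis.** Protocol 8.4.3: "PK parameters will be analysed after logarithmic transformation". SAP 7.2.9 is looser and commits to the log scale for at least AUC and Cmax. Both PTF indices are marked for statistical analysis and listed among the main PK variables of interest (Protocol 8.4.3, SAP 8.4.3). Neither is the primary variable (AUC0-24) or the secondary one (Cmin,tau).

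**The concern.** A peak-trough index should fall when troughs rise. If its trough is a sample drawn before any levodopa was given, it cannot respond to what happens between doses. It then reports only how far the peak stands above the average.

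This matters because a steadier levodopa profile is the reason given for the MR formulation (Protocol 1.1), and the PK results are to select the combination for later studies (Protocol 2.1). A diluted fluctuation index would understate the advantage of MR over Sinemet in Group 4. In every group it would also be blind to trough changes brought about by carbidopa or ODM-104.

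A second weakness lies in PTFtau. If the highest concentration in an interval is its last sample, then Cmax,tau = Cmin,tau and PTFtau is exactly 0. Zero has no logarithm, so a log-scale model loses the observation.

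**Working it through.** The plan states no figure for PTF0-16, so there is none to reproduce.

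**1. What the literal rule gives (algebra only)**
- Samples within 0-16 h: 0, then every 0.5 h to 14 h, then 15 and 16 h, which makes 1 + 28 + 2 = 31. The 0 h sample is one of them.
- Levodopa at 0 h: at least 4 days of wash-out plus six levodopa-free days (days 1-6), so about 0 apart from any endogenous level, which the documents do not give.
- With Cmin = 0, PTF0-16 = 100 × (Cmax − 0)/Cav = 100 × Cmax/Cav, for every treatment.

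**2. Size of the effect (assumed kinetics)**

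Model: one compartment, first-order absorption, equal doses at 0, 3.5, 7 and 10.5 h, protocol sampling times, linear trapezoid for AUC0-16. Assumptions not in the documents: IR ka 2-3/h and half-life 1.5 h; MR ka 0.5-0.8/h, half-life 2-2.5 h and lag 0.25 h.

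| Cmin used | IR | MR | MR below IR |
|---|---|---|---|
| Literal (0 h sample, about 0) | 164-177% | 140-142% | about 15-20% |
| Lowest of the 3.5, 7, 10.5 and 14 h values | 114-131% | 74-78% | about 32-43% |
| Lowest from 3.5 h to 16 h | 139-155% | 74-84% | about 46-49% |

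Pairing the rounded extremes gives 1 − 142/164 = 13% to 1 − 140/177 = 21% for the first row, and 1 − 78/114 = 32% to 1 − 74/131 = 44% for the second.

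**3. A wider grid**

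Forty assumed scenarios: IR/MR half-life pairs 1.5/1.5, 1.5/2, 1.5/2.5, 2/2 and 2/3 h; IR ka 2 or 4/h; MR ka 0.55, 0.8 or 1.2/h without lag, or 0.8/h with a 0.25 h lag. The comparison is with the lowest-trough version.
- The IR-MR contrast shrank in all 40.
- Share kept on the log scale: 31-51%, median 43%.
- Share kept in absolute points: 53-76%, median 68%.
- One scenario in full (half-lives 1.5 and 2 h, ka 2 and 0.8/h, no lag): literal 164 against 141, ratio 1.17, difference 24 points; lowest trough 114 against 77, ratio 1.49, difference 38 points (differences from unrounded values). Log share kept: ln 1.17/ln 1.49 = 0.157/0.399 = 39%. Absolute share kept: 24/38 = 63%.

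**4. Choosing the replacement**
- Dropping only the 0 h sample is not enough. The 0.5 h sample on the first rise can then become Cmin. In one scenario this gave IR 119% and MR 123%, ratio 0.96, reversing the contrast.
- Running the window to 16 h puts the IR minimum at the 16 h sample, 5.5 h after the last dose and outside every 3.5 h dosing interval. Most of the MR minima stay at 3.5 h. That compares terminal wash-out with a first trough and inflates the contrast.
- The lowest Cmin,tau avoids both faults.

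**5. Zeros in PTFtau**

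Assumptions: MR ka 0.4-0.8/h, lag 0.25-1 h, 30% variation in ka, 20% in half-life, 10% assay noise. About 6-55% of first MR intervals had their maximum at the 3.5 h sample; nearby runs gave 5-61%. Later MR intervals gave 0-30%, and IR gave none. Slower absorption and longer lag raise the share.

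**The case against.** **The plan never says that the pre-dose sample is the trough.** This is correct. A reader might infer a deliberate rule, but the documents only leave the term undefined. Table 4 shows that the sponsor distinguishes post-dose minima elsewhere, so the analyst may well intend one here. The text still supports no choice other than the observed minimum, so a definition is needed.

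**The index still separates the formulations.** This also stands. A reader might infer that PTF0-16 hides most of the MR-IR difference or cannot show a steadier profile. The literal index still put MR below IR in every scenario and usually kept most of the absolute contrast. The heavier loss is on the log scale, and every size here rests on kinetic values that the documents do not supply.

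**Other measures cover the question.** Cmax/Cmin,tau, Cmax/Cmin,tau,actual, Cmax/C(16h) and PTFtau use post-dose concentrations and are analysed. Conclusions also draw on the whole concentration-time profiles (Protocol 8.1). MR is compared with IR within subject only in Group 4. This limits the consequence but does not repair the index.

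**The PTFtau losses are not certain.** SAP 7.2.9 leaves the scale partly open, and SAP 7.2.8 allows another transformation or non-parametric methods after residual checks. In noise-free profiles with a 0.25 h lag, no MR case peaked at 3.5 h. A reader might also infer that the lost intervals are the flattest profiles; in the first interval they are profiles still rising at 3.5 h. What stands is that Protocol 8.4.3 states the log scale without exception, and neither document says how a zero is handled.

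**Conclusion.** The point holds as a missing definition whose literal reading gives the wrong quantity. That PTF0-16 then equals 100 × Cmax/Cav follows from the dosing and sampling schedule alone, provided that pre-dose levodopa is about 0.

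The size is illustrative. Under the assumed kinetics, MR appears about 15-20% below IR instead of about 32-43%, and typically more than half of the log-scale contrast disappears. The documents do not support saying that MR's steadier profile would go undetected, or that the primary or secondary analysis is affected.

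The PTFtau weakness is separate. It is real if the Protocol's log rule is followed. In these simulations it removed observations from MR intervals only, so the loss would be one-sided. How often this happens depends on absorption rate and lag, which the documents do not give.

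The change should be made: both indices are among the main PK variables of interest, and it costs almost nothing.

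**What to change.** - **PTF0-16.** In Protocol Table 4 and SAP 8.4, define its Cmin as the lowest of the four end-of-interval concentrations Cmin,tau (3.5, 7, 10.5 and 14 h). This excludes the pre-dose, first-rise and 16 h wash-out samples. Cmax/C(16h) already covers the 16 h sample.
- **PTFtau.** State in SAP 7.2.9 or 8.4 that it is analysed untransformed, or by a method that keeps zeros, and report the number of zeros by treatment and interval.
- **Cost.** One sentence for each index and a small programming change, with no new samples or subjects. PTF0-16 values will not match any earlier study that used the literal definition. An untransformed PTFtau analysis gives differences in percentage points instead of geometric mean ratios.

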6.3 Pharmacogenomic variables

A blood sample for DNA extraction will be collected once between the day 1 of the first study period and the end-of-study visit from those subjects who agree to take part in the optional study-related exploratory PG study. A separate IC is required from the subject participating in this PG study. DNA from these subjects will be stored in the sponsor's sample repository until analysis.

The objective of exploratory DNA analysis is to investigate possible factors that may give supportive information related to the absorption, distribution, metabolism, excretion, pharmacodynamics and safety of ODM-104, its metabolites or other drug treatments given in this study.

Instructions for the collection, handling, storage and transportation of samples will be provided before the start of the study.

6.4 Safety assessments

6.4.1 Adverse events

6.4.1.1 Definitions

An **AE** is any untoward medical occurrence in a study subject administered a pharmaceutical product and which does not necessarily have a causal relationship with this treatment. An AE

can therefore be any unfavourable and unintended sign (including an abnormal laboratory finding), symptom, or disease temporally associated with the use of an investigational medicinal product, whether or not related to the investigational medicinal product. The definition also covers medication errors and uses outside what is foreseen in the protocol, including misuse and abuse of the product.

Thus, an AE may be an appearance or worsening of any undesirable sign or symptom, any worsening of the current medical conditions or onset of a new disease, compared with the previous observations or a clinically significant adverse change in a laboratory variable or other diagnostic finding (e.g. ECG).

An SAE is any untoward medical occurrences that at any dose

- results in death
- is life-threatening
- requires inpatient hospitalisation or prolongation of existing hospitalisation
- results in persistent or significant disability/incapacity
- is a congenital anomaly/birth defect, or
- is an important medical event jeopardizing the patient or requiring intervention to prevent serious outcome (examples of such events are intensive treatment in an emergency room or at home for allergic bronchospasm; blood dyscrasias or convulsions that do not result in hospitalisation; development of drug dependency or drug abuse; overdose or interaction)

Other significant AEs are AEs (other than those meeting the definition of serious) that are of clinical importance and lead to:

- a diagnostic or therapeutic intervention
- discontinuation of the investigational medicinal product
- reduction of its dose
- significant additional concomitant treatment, or
- marked haematological and other laboratory abnormalities

